#### 3.2.1.5 *ECG*

ECG results will be listed at each assessment by treatment group and subject, for core trial and additional cycles separately. Any unscheduled ECG will be flagged [U] in the listing.

The baseline will be defined as the last available (and reliable if applicable) assessment collected prior to first IMP administration.

In case of triplicate ECGs, the mean will serve as analysable data.

#### 3.2.1.6 *Holter ECG*

Holter ECG results will be listed at each assessment by treatment group and subject. Any unscheduled Holter ECG will be flagged [U] in the listing.

#### 3.2.1.7 *ECOG*

ECOG will be summarised by treatment group at each scheduled assessment and will be listed at each assessment by treatment group and subject, for core trial, additional cycles and follow-up long term separately.

#### 3.2.1.8 *Serum and urine pregnancy tests*

Results for serum and urine pregnancy tests will be summarised by treatment group at each scheduled assessment and will be listed at each assessment by treatment group and subject, for core trial and additional cycles separately.

#### 3.2.1.9 *Specific renal safety biomarkers*

CCI

### 3.2.2 *Missing data and outliers*

#### 3.2.2.1 *Missing data*

No missing value will be replaced.

If a value required a retest, the last reliable non-missing value will be taken into account if measured before the first administration of IMP; and the first non-missing reliable value for post-baseline assessments. An assessment will be considered reliable if it is performed without any technical problem and if the result is within the range of plausible values.

Any repeat or additional assessments performed will be included in the individual subject data listings.

If there is a significant number of missing values for a subject (or if there is confirmed data appearing spurious), a decision will be made following consultation with the sponsor regarding the handling of these data in summaries, prior to database freeze.

#### 3.2.2.2 *Missing or incomplete dates*

In all listings, missing or incomplete dates should be left as they have been recorded. However, for calculation / sorting / assignation based on dates, the following methods will be used:

The most conservative approach will be systematically considered (i.e. if the onset date of an AE/concomitant medication is missing / incomplete, it is assumed to have occurred during the study treatment phase (e.g. a TEAE for AEs) except if the partial onset date or other data [stop date, ...] indicates differently).

A missing/incomplete date of medical history or disease diagnosis will be assumed to have occurred before any study treatment.

Where this is possible, the derivations based on a partial date will be presented as superior inequalities (e.g. for an AE started in FEB2004 after the administration performed on 31JAN2004, the days since last dose will be “ $\geq 2$ ”, similarly the duration of ongoing AEs or medication will be “ $\geq xx$ ” according to the start and last visit dates).

### 3.2.2.3 *Outliers*

Any outlier identified prior to database lock which is impossible/unplausible will be excluded from the analysis. For other identified outliers, the impact should be assessed by performing the statistical analysis with the actual values and at least one other analysis eliminating or reducing the outlier effect.

### 3.2.3 *Subject disposition*

The number of subjects screened, included, discontinued and completed at each step of the study (core trial, additional cycles and long-term follow-up) will be tabulated by treatment group and overall on the screened population for core trial and on the included population for additional cycles and long-term follow-up and corresponding information will be listed. The number of subjects exposed and impacted by COVID-19 pandemic as well as the number of discontinued subjects due to COVID-19 will be also tabulated by treatment group and overall, by pooling core trial, additional cycles and long-term follow-up.

The number of subjects included in each analysis population will be presented by treatment group and overall for the safety population.

A listing of the inclusion and exclusion criteria not met will be provided by treatment group and subject and subject eligibility will also be listed.

The reasons for subject exclusions from each population will also be tabulated by treatment group and overall on the included population.

A summary table will present the extent of subject duration in the study for each treatment group and overall on the included population, for both core trial and long-term follow-up. The definition of the length of study duration is calculated from the date of informed consent form to the last study visit in each period.

A listing of dates of assessments and dates of hospitalisation will be presented by subject for each treatment group, for core trial, additional cycles and long-term follow-up separately. The number and percentage of subjects at each planned visit during the study will be presented by treatment group and overall for the included population, for core trial, additional cycles and long-term follow-up separately.

A listing of subjects screened but not included with the reason for screen failure will be presented by subject.

### 3.2.4 *Withdrawals*

Discontinued subjects will be listed with their reasons for withdrawal and a summary table of the number and percentage of subjects who withdrew from the study and the reasons for withdrawal will be presented by treatment group and overall for the included population, for core trial, additional cycles and long-term follow-up separately.

### **3.2.5 *Demographic and baseline characteristics***

The baseline will be defined as the last available (and reliable if applicable) assessment collected prior to first IMP administration.

All demographic (sex, race and ethnicity) and baseline characteristics (age, height, body weight and BMI at baseline) as well as postmenopausal status will be listed by treatment group and subject.

Summary statistics will be provided for demographic and baseline characteristics by treatment group and overall on the included population.

### **3.2.6 *Medical and surgical history***

Medical and surgical history will be coded using MedDRA latest version at Ipsen coding department at the time of database lock.

Listing will present the primary system organ class, the preferred term and the reported term. The listing will be sorted by treatment group, subject, start date, primary system organ class, preferred term and reported term.

A frequency table of the number and percentage of subjects will be provided for all medical and surgical history by primary system organ class and preferred term for each treatment group and overall for the included population.

### **3.2.7 *Baseline signs and symptoms related to studied disease or previous studied disease therapy***

Baseline signs and symptoms will be coded using MedDRA latest version at Ipsen coding department at the time of database lock.

Listing will present the primary system organ class, the preferred term and the reported term. The listing will be sorted by treatment group, subject, start date, primary system organ class, preferred term and reported term.

A frequency table of the number and percentage of subjects will be provided for all baseline signs and symptoms by primary system organ class and preferred term for each treatment group and overall for the included population.

### **3.2.8 *Prior chemotherapy for studied disease***

Prior chemotherapy for studied disease will be coded using WHO-DD with the latest version at Ipsen coding department at the time of database lock. The therapeutic class will correspond to the second level of Anatomic Therapeutic Class (ATC) code, which corresponds to the first three digits.

Listing will be presented for the therapeutic class, preferred name and reported name. The listing will be sorted by treatment group, subject, chronological start date, therapeutic class, preferred name and reported name.

A frequency table of the number and percentage of subjects with at least one prior chemotherapy for studied disease will be provided by therapeutic class and preferred name for each treatment group and overall on the included population.

### **3.2.9 *Prior immunotherapy for studied disease***

Prior immunotherapy for studied disease will be coded using WHO-DD with the latest version at Ipsen coding department at the time of database lock. The therapeutic class will correspond to the second level of Anatomic Therapeutic Class (ATC) code, which corresponds to the first three digits.

Listing will be presented for the therapeutic class, preferred name and reported name. The listing will be sorted by treatment group, subject, chronological start date, therapeutic class, preferred name and reported name.

A frequency table of the number and percentage of subjects with at least one prior immunotherapy for studied disease will be provided by therapeutic class and preferred name for each treatment group and overall on the included population.

### **3.2.10 *Prior radiotherapy for studied disease***

Listing will present the primary system organ class, the preferred term and the reported term. The listing will be sorted by treatment group, subject, start date, primary system organ class, preferred term and reported term.

A frequency table of the number and percentage of subjects with at least one prior radiotherapy and by number of radiotherapies will be provided by treatment group and overall on the included population.

### **3.2.11 *Prior surgical procedures for studied disease***

Prior surgical procedures for studied disease will be coded using MedDRA Dictionary with the latest version at Ipsen coding department at the time of database lock.

Listing will present the primary system organ class, the preferred term and the reported term. The listing will be sorted by treatment group, subject, start date, primary system organ class, preferred term and reported term.

A frequency table of the number and percentage of subjects with at least one prior surgical procedure for studied disease will be provided by primary system organ class and preferred term for each treatment group and overall for the included population.

### **3.2.12 *Studied disease***

A frequency table of the number and percentage of subjects in each type of disease will be provided by treatment group and overall on the included population.

Moreover, the following tumour characteristics will also be described by type of studied disease, by treatment group and overall on the included population:

- For PDAC:
  - Time since diagnosis (in months),
  - Time since first relapse after last treatment (in months),
  - Histological grade,
  - Mutation status,
  - TNM staging at first diagnosis and at last relapse.
- For CRC:
  - Time since diagnosis (in months),
  - Time since first relapse after last treatment (in months),
  - Location of the primary tumour,
  - Histological grade,
  - Mutation status,
  - TNM staging.
- For GC:
  - Time since diagnosis (in months),

- Time since first relapse after last treatment (in months),
- Location of the primary tumour,
- Type of tumour,
- Histological grade,
- Helicobacter pylori infection status,
- Mutation status,
- TNM staging.
- For GIST:
  - Time since diagnosis (in months),
  - Time since first relapse after last treatment (in months),
  - Location of the primary tumour,
  - Type of tumour,
  - Histological grade,
  - Helicobacter pylori infection status,
  - TNM staging.
- For SCCHN:
  - Time since diagnosis (in months),
  - Time since first relapse after last treatment (in months),
  - Location of the primary tumour,
  - Histological grade,
  - Viral infection status,
  - Mutation status,
  - TNM staging.
- For ES:
  - Time since diagnosis (in months),
  - Time since first relapse after last treatment (in months),
  - Location of the primary tumour (axial skeleton/appendicular skeleton),
  - Histological grade,
  - Mutation status,
  - TNM staging.

All information on the studied disease will be listed by treatment group and subject.

### 3.2.13 ***Subject compliance***

All treatment administration information will be listed by treatment group and subject, for core trial and additional cycles separately.

Number of cycles and cumulative therapeutic dose as well as overall cumulative dose (including the screening dose) will be also described by treatment group, for core trial and additional cycles separately.

Duration of each cycle as well as duration of study drug exposure in core trial and additional cycles will be also summarised.

All protocol deviations, defined prior to database freeze, will be listed by treatment group and subject, for core trial, additional cycles and long-term follow-up separately.

Major protocol violations will be summarised on the included population, for core trial, additional cycles and long-term follow-up separately.

Additionally, protocol deviations due to COVID-19 (minor and major separately) will be summarised on the included population, by pooling core trial, additional cycles and long-term follow-up.

### **3.2.14 *Prior and concomitant medications***

Prior and concomitant medications will be coded using WHO-DD with the latest version at Ipsen coding department at the time of database lock. The therapeutic class will correspond to the second level of Anatomic Therapeutic Class (ATC) code, which corresponds to the first three digits.

The date and time of first study drug administration will be used as the cut-off date for the definition of prior and concomitant medications. A medication that started before study drug administration and is continuing at time of study drug administration will be considered as both, prior and concomitant. Prior, concomitant and both prior and concomitant medications will be flagged P, C and PC respectively, in all listings.

In the event of incomplete start date and/or stop date which will not allow the categorisation of medication, it will be considered as concomitant.

Listing will be presented for the therapeutic class, preferred name and reported name. The listing will be sorted by treatment group, subject, chronological start date, therapeutic class, preferred name and reported name, for core trial, additional cycles and long-term follow-up separately.

A frequency table of the number and percentage of subjects with at least one prior medication will be provided by therapeutic class and preferred name for each treatment group and overall.

A frequency table of the number and percentage of subjects with at least one concomitant medication will be provided by therapeutic class and preferred name for each treatment group and overall on the included population, for core trial, additional cycles and long-term follow-up separately.

### **3.2.15 *Concomitant medications for studied disease***

Concomitant medications for studied disease will be coded using WHO-DD with the latest version at Ipsen coding department at the time of database lock. The therapeutic class will correspond to the second level of Anatomic Therapeutic Class (ATC) code, which corresponds to the first three digits.

Listing will be presented for the therapeutic class, preferred name and reported name. The listing will be sorted by treatment group, subject, chronological start date, therapeutic class, preferred name and reported name, for core trial, additional cycles and long-term follow-up separately.

A frequency table of the number and percentage of subjects with at least one concomitant medication for studied disease will be provided by therapeutic class and preferred name for each treatment group and overall on the included population, for core trial, additional cycles and long-term follow-up separately.

### **3.2.16 *Prior and concomitant non-drug therapies***

Prior and concomitant non-drug therapies will be coded using MedDRA Dictionary with the latest version at Ipsen coding department at the time of database lock.

The date and time of first study drug administration will be used as the cut-off date for the definition of prior and concomitant therapies. A therapy that started before study drug administration and is continuing at time of study drug administration will be considered as both, prior and concomitant. Prior, concomitant and both prior and concomitant therapies will be flagged P, C and PC respectively, in all listings.

In the event of incomplete start date and/or stop date which will not allow the categorisation of therapy, it will be considered as concomitant.

Listing will present the primary system organ class, the preferred term and the reported term. The listing will be sorted by treatment group, subject, start date, primary system organ class, preferred term and reported term, for core trial, additional cycles and long-term follow-up separately.

A frequency table of the number and percentage of subjects with at least one prior non-drug therapy will be provided by therapeutic class and preferred name for each treatment group and overall.

A frequency table of the number and percentage of subjects with at least one concomitant non-drug therapy will be provided by primary system organ class and preferred term for each treatment group and overall for the included population, for core trial, additional cycles and long-term follow-up separately.

### **3.2.17 Concomitant surgical procedures**

Concomitant surgical procedures will be coded using MedDRA Dictionary with the latest version at Ipsen coding department at the time of database lock.

Listing will present the primary system organ class, the preferred term and the reported term. The listing will be sorted by treatment group, subject, start date, primary system organ class, preferred term and reported term, for core trial, additional cycles and long-term follow-up separately.

A frequency table of the number and percentage of subjects with at least one concomitant surgical procedure will be provided by primary system organ class and preferred term for each treatment group and overall for the included population, for core trial, additional cycles and long-term follow-up separately.

### **3.2.18 Pharmacodynamics/efficacy analyses**

All information related to tumour assessment according to RECIST criteria v1.1 will be listed by treatment group and subject, for core trial, additional cycles and long-term follow-up separately.

#### **3.2.18.1 Best Overall Response**

The BOR will be presented by treatment group at the end of the core trial, at the end of the additional cycles and at the end of the long-term follow-up.

BOR will be derived as the highest objective response achieved by the subject based on measurable lesions ((i.e. target, non-target and new lesions) from the time of first treatment until disease progression or the end of period and will be classified as: CR > PR > Non-CR/Non-PD (NCR/NPD) > SD > PD > NE.

If SD is believed to be the best response, it must also meet the minimum time from baseline of 56 days. If the minimum time is not met, the subject's best response will be based on the subsequent assessments.

According to RECIST guideline, any response CR or PR must be confirmed at least 4 weeks later, or as close to this timepoint as possible.

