5.2 Exclusion Criteria (Phase I/II)

Eligible subjects must not have any of the following:

- (1) Prior treatment received:
 - (a) Any antitumour treatment since last documented disease progression

- (b) Any chemotherapy within 3 weeks or nitrosourea within 6 weeks prior to first treatment IMP administration
- (c) Any curative radiotherapy within 4 weeks, or palliative radiotherapy within 7 days prior to first treatment IMP administration
- (d) Any monoclonal antibodies within 4 weeks or tyrosine kinases inhibitors within 2 weeks prior to the first treatment IMP administration
- (e) Any other IMP within 2 weeks prior to first treatment IMP administration, if the previous compound is a mechanism-based molecularly targeted agent whose $t_{1/2}$ is not well-characterised.
- (2) Brain metastases.
- (3) Nephrectomy, renal transplant or concomitant nephrotoxic therapy putting the subject at high risk of renal toxicity during the study.
- (4) Only nonmeasurable metastatic bone lesions.
- (5) Existing or planned colostomy during study participation.
- (6) Any history of inflammatory bowel disease.
- (7) Any uncontrolled significant medical, psychiatric or surgical condition or laboratory finding, that would pose a risk to subject safety or interfere with study participation or interpretation of individual subject results.
- (8) Clinically significant abnormalities on ECG at screening including corrected QT interval (Fridericia's formula) >450 msec for males or 470 msec for females at screening.
- (9) Previously received external beam irradiation to a field that includes more than 30% of the bone marrow or kidneys.
- (10) Criterion 10 is removed by protocol amendment.
- (11) Any unresolved NCI-CTCAE Grade 2 or higher toxicity (except alopecia) from previous antitumour treatment and/or medical/surgical procedures/interventions.
- (12) Known allergy to IMP or its excipients administered in this study, including imaging contrast media.
- (13) Positive pregnancy test (female subjects).
- (14) Likely to be uncompliant or uncooperative during the study, in the judgment of the investigator.
- (15) Unable to understand the nature, scope and possible consequences of the study, in the judgment of the investigator.
- (16) Sponsor employees or investigator site personnel directly affiliated with this study, and their immediate families. Immediate family is defined as a spouse, parent, child or sibling, whether biological or legally adopted.

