10.1.2 Phase I Imaging Assessments

Radiological assessments for tumour response will be performed as per schedule of assessment (Attachment 1, Section 19.1.) as well as when clinically indicated. Additionally, in the event of biological or clinical signs of disease progression further radiological assessments can be done based upon the investigator's judgment.

For PDAC, CRC, GC and GIST, chest/abdomen/pelvis scans are required and can be performed in two images if required; from chest to abdomen and from abdomen to pelvis. The scans should extend from the lateral ends of the clavicles (to ensure complete coverage of lung apices) down to the lesser trochanters or caudally thereof (to ensure complete coverage of inguinal lymph nodes). For abdominal/pelvic scans, the scan should begin cranially at the right dome of the

diaphragm and extend down to the lesser trochanters or caudally thereof (to ensure complete coverage of inguinal lymph nodes).

For SCCHN, scans from head to pelvis are required and can be performed in three images if required; from head to chest, from chest to abdomen and from abdomen to pelvis).

For ES subject, whole body scans will be performed at screening to assess the localization of the targeted lesions. In case of lesions outside of the usual acquisition areas (chest to pelvis), the number of bed positions will be adapted accordingly for further assessment.

¹⁸F-FDG-PET images will be assessed locally and the results for screening and EOCT visit will be collected in the eCRF.

After the EOCT, ED or EOAC visit, subjects will be followed up every 3 months (± 2 weeks) to further evaluate the efficacy (by CT or MRI) until disease progression, administration of any other chemotherapy or radiotherapy, lost to follow-up, withdrawal of consent, death or a maximum of 2 years, whichever occurs first (see Section 6.2.3). After disease progression is confirmed, no further CT/MRI scans will be required for tumour/disease assessment. The survival status and safety of the subjects will continue to be monitored as indicated in Section 8.1.2.3 until lost to follow-up, withdrawal of consent, death or a maximum of 5 years, whichever occurs first.

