4.4. Evaluation of best overall response

The best overall response is the best response recorded from the start of the study treatment until the end of treatment taking into account any requirement for confirmation. On occasion a response may not be documented until after the end of therapy so protocols should be clear if post-treatment assessments are to be considered in determination of best overall response. Protocols must specify how any new therapy introduced before progression will affect best response designation. The patient's best overall response assignment will depend on the findings of both target and non-target disease and will also take into consideration the appearance of new lesions. Furthermore, depending on the nature of the study and the protocol requirements, it may also require confirmatory measurement (see Section 4.6). Specifically, in non-randomised trials where response is the primary endpoint, confirmation of PR or CR is needed to deem either one the 'best overall response'. This is described further below.

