### 3.2.18.4 Progression-Free Survival

The PFS according to local review will include investigator assessed PD and deaths. Other data will be censored. PFS will be assessed at the end of the core trial, at the end of the additional cycles and at the end of the long-term follow-up.

Definition of progression date:

The PD date is assigned to the first time at which PD can be declared.

Definition of censoring date:

Censoring dates are defined in subjects with no PD or death before end of period or withdrawal. In these subjects, the censoring date is defined as the last date on which progression status was 'adequately' assessed. This is taken to be the date of the last radiological assessment at which the target lesions were evaluated by local investigator review.

If no PD is documented, patient will be censored at the last available overall tumour assessment before start of the new anticancer therapy.

Definition of PFS time:

The PFS time will be calculated as the time from first treatment administration to either locally assessed PD or death.

$$\text{PFS time} = [(\text{Date of event} - \text{date of first treatment administration}) + 1] / 7 \text{ (weeks)}$$

The distribution of PFS times will be estimated using the Kaplan-Meier (KM) product limit method.

The Kaplan Meier method will provide hazard curves, life tables, median as well as corresponding 95% Confidence Interval (CI). These statistics will be presented for each treatment group.

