## 7 APPENDICES TO THE SAP

### Appendix 1: Derived Data

The following derived data will be calculated:

- Study day

Study day will be defined as ‘-1’ for the day prior to first IMP administration during core trial and as ‘1’ for the day of first IMP administration during core trial (i.e. day 0 does not exist).

- BMI

BMI (kg/m^2) will be derived as  $\text{Weight (kg)} / [\text{Height(cm)} / 100]^2$  and rounded to the nearest decimal.

- Core trial duration

Core trial duration (days) will be calculated as (date of last visit attended during core trial - date of informed consent form) + 1.

- Long-term follow-up duration

Long-term follow-up duration (days) will be calculated as (date of last visit attended during long-term follow-up - date of informed consent form) + 1.

- Time since diagnosis

Time since diagnosis in months will be calculated as (date of informed consent form - date of diagnosis) + 1] / 30.4375.

- Time since first relapse after last treatment

Time since first relapse after last treatment in months will be calculated as (date of informed consent form - date of first relapse after last treatment) + 1] / 30.4375.

- Baseline

Baseline will be derived as the last available (and reliable if applicable) assessment before first IMP administration.

- Changes from baseline

Changes from baseline will be calculated as the difference from baseline (e.g. assessment at the visit – assessment at baseline).

- Duration of each cycle

Duration of each cycle (days) will be calculated as (date of infusion of the next cycle - date of infusion of the cycle) + 1.

For last cycle, duration will be calculated as (date of Day 29 of last cycle - date of infusion of the cycle) + 1.

- Study drug exposure during core trial

Study drug exposure (days) = (date of infusion of last cycle during core trial - date of infusion of cycle 1) + 29 days.

- Study drug exposure during additional cycles

Study drug exposure (days) = (date of infusion of last cycle during additional cycles - date of infusion of first cycle during additional cycles) + 29 days.

- Progression-Free Survival

PFS time (weeks) = [(Date of event – date of first treatment administration) + 1] / 7.

Event	Decision	Date of event or censoring to consider for the analysis
Progression Disease	Not censored	Date of progression
No event	Censored	Last date of tumour assessment
Death	Not Censored	Date of death

- Overall survival

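### Best overall response has no cut at new antitumour therapy, so a confirmed response after a switch without progression would count for the study drug in the end-of-follow-up ORR; the two PFS censoring rules also disagree

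*SAP*

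**What the plan says.** **Response.** SAP 3.2.18.1 takes BOR as the best response "from the time of first treatment until disease progression or the end of period". It is presented "at the end of the core trial, at the end of the additional cycles and at the end of the long-term follow-up", and "any response CR or PR must be confirmed at least 4 weeks later", or as near to that as possible. SAP 3.2.18.2 and 3.2.18.3 take ORR and DCR directly from BOR. None of the three sections mentions new therapy.

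**Follow-up imaging.** Protocol 10.1.2 continues CT or MRI every 3 months "until disease progression, administration of any other chemotherapy or radiotherapy, lost to follow-up, withdrawal of consent, death or a maximum of 2 years". Protocol 6.2.3, Protocol Table 8 footnote b and SAP Table 1 footnote b use the same restricted pair of treatments.

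**Treatment classes.** Exclusion criterion 1 (Protocol 5.2) deals with chemotherapy in (b) and radiotherapy in (c), and has a separate item (d): "Any monoclonal antibodies within 4 weeks or tyrosine kinases inhibitors within 2 weeks prior to the first treatment IMP administration". SAP 3.2.8 to 3.2.11 tabulate prior chemotherapy, immunotherapy, radiotherapy and surgery separately.

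**Attached standard.** The RECIST 1.1 text in Protocol Attachment 4 (its section 4.4) says: "Protocols must specify how any new therapy introduced before progression will affect best response designation".

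**PFS.** SAP 3.2.18.4 says: "If no PD is documented, patient will be censored at the last available overall tumour assessment before start of the new anticancer therapy". For a subject with no event, the PFS table in Appendix 1 gives the censoring date as "Last date of tumour assessment", without reference to new therapy.

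**The concern.** A response rate for a study drug should rest on scans taken before another active treatment could have produced the shrinkage. Here the window runs on into follow-up, and the scans that feed it do not stop for every class of new treatment. A subject with stable disease at the end of core trial (EOCT) who starts a kinase inhibitor or antibody in follow-up, and shrinks on it, would become a responder to 177Lu-3BP-227. The attached RECIST text asks for an explicit rule, and neither document gives one for response. The SAP does have a new-therapy rule for PFS, so the omission is specific to BOR, ORR and DCR.

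For PFS, two parts of the SAP describe the same derivation differently. A programmer following one would get a different censoring date from a programmer following the other.

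**Working it through.** The plan states no figure that depends on this rule, so there is none to reproduce. The check compares the passages and then sizes one hypothetical case.

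**1. When can other therapy overlap with a BOR scan?** Protocol 6.3.1 prohibits other antitumour treatment until 6 weeks after the last dose. With the second dose on study Day 29 (28 days after the first), that period ends on Day 29 + 42 = Day 71. The EOCT visit is Day 43 of Cycle 2, nominally the same Day 71. The end-of-additional-cycles visit is likewise 6 weeks after the last dose. Both scans are protected at their nominal day. Long-term follow-up scans, for up to 2 years, are not.

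**2. Do follow-up scans matter for BOR?** Yes. The core trial schedules one post-baseline CT/MRI, at EOCT. With confirmation required at least 4 weeks later, the confirming scan for a subject without additional cycles normally falls in follow-up.

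**3. What happens on the wording as written?** Take a subject with stable disease at EOCT who starts a kinase inhibitor in follow-up without progression. The treatment is neither chemotherapy nor radiotherapy as exclusion criterion 1 divides them, so scanning continues. Partial response at month 6, confirmed at month 9, becomes the BOR.

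**4. Size of one such case**, as x/n with exact 95% intervals (the method named in Protocol 12.2.2):

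| n | ORR with the case | ORR with a cut | Shift (points) |
|---|---|---|---|
| 3 | 1/3 = 33.3% (0.8 to 90.6) | 0/3 = 0% (0 to 70.8) | 33.3 |
| 4 | 1/4 = 25.0% (0.6 to 80.6) | 0/4 = 0% (0 to 60.2) | 25.0 |
| 5 | 1/5 = 20.0% (0.5 to 71.6) | 0/5 = 0% (0 to 52.2) | 20.0 |
| 30 | 1/30 = 3.3% (0.1 to 17.2) | 0/30 = 0% (0 to 11.6) | 3.3 |

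The table assumes no other responder. The shift is 1/n whatever the number of other responders. DCR follows the same rule but moves less often: a subject already stable at EOCT counts as controlled with or without the later response.

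**5. PFS, no progression and no death.** Take the same subject, scanned to the 2-year limit without an event. SAP 3.2.18.4 censors at EOCT: 71/7 = 10.1 weeks. Appendix 1 censors at the last scan, which can be as late as (71 + 730)/7 = 801/7 = 114.4 weeks.

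**6. PFS, death after new therapy without documented progression.** Assume stable disease at EOCT, new therapy at week 14 and death at week 60. SAP 3.2.18.4 opens by counting deaths as events and defines censoring for subjects with neither progression nor death; on that reading, as in Appendix 1, this is an event at 60 weeks. Its final censoring sentence depends only on the absence of documented progression; read literally, it gives 10.1 weeks, censored. The ambiguity lies within 3.2.18.4.

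**The case against.** The strongest case against is about consequence. The affected group is narrow: subjects enter with unresectable, locally advanced or metastatic disease and no further suitable options (Protocol 5.1.1), documented progression closes the BOR window, and a false credit needs a switch without progression, to a class other than chemotherapy or radiotherapy, followed by a confirmed response. Phase I ORR is secondary and descriptive. Chemotherapy may be meant loosely, since the SAP has no prior-therapy heading for kinase inhibitors. A separate image review charter, not available here, may contain a rule. Phase II on-treatment scans already stop at any new antitumour treatment (Protocol 10.1.3), although the follow-up paragraph there returns to the narrower pair, and this SAP covers phase I dose escalation only.

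The narrowness stands, and it limits the size. It does not supply the missing rule: the SAP defines the BOR window itself, and a loose meaning of chemotherapy cannot be assumed when exclusion criterion 1 separates the classes.

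A reader might infer that contaminated responses would drive the choice of phase II design. The documents do not support that. The choice follows completion of dose escalation (Protocol 4.2.1.4), the interim is at the end of the core trial (SAP 3.2.24), and the main report uses data to the last EOCT visit, with later data in an addendum (Protocol 12.2.9).

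A reader might also infer that 3.2.18.4 definitely censors a late death that Appendix 1 counts. It does not: its own opening counts deaths, so that conflict is an ambiguity. Counting such deaths is in itself a legitimate choice.

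**Conclusion.** The point holds in a limited form. As written, BOR, ORR and DCR at the end of long-term follow-up can include responses that arose on a later treatment of another class. The EOCT and end-of-additional-cycles scans are largely protected by the prohibition period. The documents do not say how many subjects will switch without progression, and the number is probably small, so the corrected ORR cannot be computed. The 20.0 to 33.3 points per cohort is the effect of one assumed case. It would be wrong to say that responses are being misattributed; they would be if the situation arose.

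The PFS conflict for subjects with no event is definite, and it needs no assumption beyond a scan after new therapy. The treatment of deaths after new therapy needs one stated rule. This is worth correcting before the follow-up analysis, but it does not threaten the primary safety objective.

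**What to change.** - **SAP 3.2.18.1 to 3.2.18.3.** Derive BOR, ORR and DCR only from assessments up to the earlier of documented progression and the start of any new antitumour treatment: any systemic class, radiotherapy, or surgery on a target lesion. List later scans without using them.
- **SAP Appendix 1, PFS table.** Change the no-event row to the last tumour assessment before the start of new anticancer therapy, to agree with 3.2.18.4.
- **SAP 3.2.18.4 and Appendix 1.** State one rule, in the same words, for deaths after new therapy without documented progression.

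The cost is SAP text and programming. Later antitumour treatment is already recorded (Protocol 6.2.3 and 6.3.1), so no new data are needed. ORR may come out slightly lower, partly because a response first seen at EOCT would stay unconfirmed if its confirming scan came after a switch. No change to the protocol's imaging schedule is required once the SAP has the cut.
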